#### **14.3.1. Severity of an Adverse Event**

Severity of AEs will be graded by the Investigator as one of:

- **Mild (Grade 1):** A type of AE that is usually transient and may require only minimal treatment or therapeutic intervention. The event does not generally interfere with usual activities of daily living.
- **Moderate (Grade 2):** A type of AE that is usually alleviated with additional specific therapeutic intervention. The event interferes with usual activities of daily living, causing discomfort but poses no significant or permanent risk of harm to the research subject.
- **Severe (Grade 3):** A type of AE that interrupts usual activities of daily living, or significantly affects clinical status, or may require intensive therapeutic intervention.
- **Life-threatening (Grade 4):** A type of AE that places the subject at immediate risk of death.
- **Death (Grade 5):** Events that result in death.

#### **14.3.2. Causal Relationship of an Adverse Event**

The Investigator will assess the relationship between study drug and the occurrence of each AE. The Investigator's assessment of the relationship of each AE to study drug will be recorded in the source documents and the eCRF. Alternative causes, such as medical history, concomitant therapy, other risk factors, and the temporal relationship of the event to the study drug should be considered and investigated, if appropriate. The following definitions are general guidelines to help assign grade of attribution:

- **Not related:** The event is clearly related to other factors such as the subject's environment or clinical state, therapeutic interventions or concomitant drugs administered to the subject. This is especially so when an event occurs prior to the commencement of treatment with the study drug.

- **Unlikely:** The temporal association, subject history, and/or circumstances are such that the study drug is not likely to have had an association with the observed event. Other conditions, including concurrent illness, progression, or expression of the disease state, or reaction to a concomitant drug administered appear to explain the event.
- **Possible:** The event follows a reasonable temporal sequence from the time of study drug administration or follows a known response to the study drug but could have been produced by other factors such as the subject's clinical state, other therapeutic interventions, or concomitant drugs administered to the subject.
- **Probable:** The event follows a reasonable temporal sequence from the time of study drug administration and follows a known response to the study drug and cannot be reasonably explained by other factors such as the subject's clinical state, other therapeutic interventions, or concomitant drugs administered to the subject.
- **Definite:** The event follows a reasonable temporal sequence from the time of study drug administration or control abates upon discontinuation or cannot be explained by known characteristics of the subject's clinical state.

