### 6.3. Summary of Potential Risks and Benefits

EXN407 is an investigational drug and the safety profile in humans has not yet been established because it has not been administered to any human subjects. It is therefore recommended that subjects are carefully monitored during administration of EXN407 until sufficient human experience is obtained to determine its safety.

Hypersensitivity reactions may occur in susceptible individuals.

No adverse reactions have been noted after *in vivo* good laboratory practice (GLP) repeat dose ocular toxicity studies in the rat and monkeys administered repeat doses of up to 0.015 mg/eye/dose (1.5 mg/mL, total dose of 0.06 mg/eye/day) and up to 0.0525 mg/eye/dose (1.5 mg/mL, total dose of 0.21 mg/eye/day), respectively (total four doses per eye per day) for 13 weeks. Total human dose in this study will be up to 0.09 mg/day (1.5 mg/mL).

As systemic absorption is anticipated to be very low based upon nonclinical data, the possibilities of direct drug related systemic adverse effects are also anticipated to be very low.

One potential benefit to subjects with a visual acuity better than an approximate Snellen equivalent of 20/32 (6/9, 78 letters) or worse than 20/160 (6/48, 39 letters) who are not offered intravitreal anti-VEGF injections, due to the lack of reimbursement from the public healthcare system for example in Australia, or who decline injection, but who do experience clear center involved DME is that they could potentially benefit from treatment that manages the VEGF165b/VEGF165a ratio in the eye.

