#### **14.7. Reporting Serious Adverse Events**

Any SAEs considered possibly or probably related to the study drug and discovered by the Investigator at any time after the study should be reported. All SAEs must be reported to the Sponsor within 24 hours of the first awareness of the event. The Investigator must complete, sign and date the SAE pages, verify the accuracy of the information recorded on the SAE pages with the corresponding source documents, and send a copy to the Sponsor.

Additional follow-up information, if required or available, should all be emailed or faxed to the Sponsor within one business day of receipt and this should be completed on a follow-up SAE form and placed with the original SAE information and kept with the appropriate section of the eCRF and/or study file.

The Sponsor is responsible for notifying the relevant regulatory authorities of certain events. It is the Investigator's responsibility to notify the IEC of all SAEs in accordance with the IEC's SAE reporting policy. The Investigator will also be notified of all unexpected, serious, drug related events that occur during the clinical trial. The investigational site is responsible for notifying its IEC of these additional SAEs.

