### **18.3.2. Adverse Event**

AEs will be coded using the most current version of the Medical Dictionary for Regulatory Activities (MedDRA®) available at the start of the study. Treatment emergent adverse events (TEAEs) will be defined as AEs that occurred or worsened following the first administration of study medication. TEAEs will be summarized separately for ocular and non-ocular TEAEs by study and contralateral eye. The number of subjects experiencing TEAEs and the number of individual TEAEs will be summarized by treatment group, study and contralateral eye, system, organ, class (SOC) and PT, including summaries by severity and relationship to study drug.

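### The causality scale in Section 14.3.2 is out of order: Definite is looser than Probable, so a new, unexplained event fits only the top grade

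*Combined protocol and SAP*

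**What the plan says.** Section 14.3.2 gives five grades: *Not related*, *Unlikely*, *Possible*, *Probable* and *Definite*. It introduces them with the words "The following definitions are general guidelines to help assign grade of attribution" and tells the investigator to consider alternative causes.

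- *Possible*: reasonable timing "or follows a known response to the study drug but could have been produced by other factors".
- *Probable*: reasonable timing "and follows a known response to the study drug and cannot be reasonably explained by other factors".
- *Definite*: the event follows in reasonable time from "study drug administration or control abates upon discontinuation or cannot be explained by known characteristics" of the subject's clinical state. The sentence contains no 'and' and no known-response condition.

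On prior experience, Section 6.3 states that "the safety profile in humans has not yet been established because it has not been administered to any human subjects". It reports no adverse reactions in the repeat-dose ocular toxicity studies in rats and monkeys, and warns that "Hypersensitivity reactions may occur in susceptible individuals".

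The grade is used in several places:

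- Section 18.3.2 tabulates treatment-emergent AEs, "including summaries by severity and relationship to study drug".
- Section 14.7 covers late reports: "Any SAEs considered possibly or probably related to the study drug and discovered by the Investigator" at any time after the study.
- Section 14.8 sets follow-up for events that are related, possibly related or probably related.
- Sections 8.5.1.1, 8.5.2.1 and 8.5.2.2 use plain 'related' or 'treatment related' in stopping criteria. Section 14.2 uses 'related' for the 30-day follow-up of AEs.

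No section says which of the five grades count as related.

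**The concern.** On an ordered scale, each step up should ask for at least as much evidence as the step below. Here the step from *Probable* to *Definite* drops a condition and replaces 'and' with 'or'.

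The event that shows this most clearly is the one a first-in-human study most needs to grade well: an unexpected event, well timed, with no competing explanation. It cannot be *Possible*, because that grade needs other factors that could have produced it. It cannot be *Probable*, because that grade needs a known response. One investigator may follow the text up to *Definite*. Another may judge *Definite* too strong and settle on *Possible*. The study may run at up to 17 centers, so a relationship table could reflect how each site resolved the wording as much as what the drug did.

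The grade names also fail to carry through. A late serious event graded *Definite* is not named in Section 14.7, and 'related' in Section 14.8 is not one of the five grades.

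**Working it through.** The plan gives no figure on this point, so there is none to reproduce. The check is one of logic.

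**Inputs (Section 14.3.2).** Each event has four yes/no features:

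- T: plausible timing
- K: known response to the drug
- E: other factors could explain it
- D: abates on discontinuation

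This gives 2 × 2 × 2 × 2 = 16 patterns. They are logical cases, not event frequencies.

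**Possible and Probable.**

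- *Possible* = (T or K) and E. T or K holds in 12 patterns, half of them with E: 6 of 16.
- *Probable* = T and K and not E: 16 / 8 = 2 of 16.

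**Definite, three readings of the sentence.**

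1. Literal: T or D or not E. It fails only when T = 0, D = 0 and E = 1, which is 2 patterns: 16 − 2 = 14.
2. T and (D or not E): 8 × 3/4 = 6.
3. (T and D) or not E: 8 + 2 = 10.

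Readings 2 and 3 take 'or control' as part of 'study drug administration or control', with a connecting word lost.

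| Reading | Meets *Definite* | *Definite* but not *Probable* | With K = 0: *Definite* / *Probable* | Timing alone, other cause present (T=1, K=0, E=1, D=0) |
|---|---|---|---|---|
| 1 | 14 | 12 | 7 / 0 | Meets *Definite* |
| 2 | 6 | 4 | 3 / 0 | Does not |
| 3 | 10 | 8 | 5 / 0 | Does not |

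Under every reading both *Probable* patterns also meet *Definite*, while most *Definite* patterns fail *Probable*.

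**The new, unexplained event with no dechallenge information (T=1, K=0, E=0, D=0).** *Possible* fails because E = 0. *Probable* fails because K = 0. *Definite* is met under readings 1, 2 and 3.

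**Effect on a related / not related split.** Take the 8 patterns with plausible timing.

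- Cut at *Possible* or higher: the 4 with E = 1 meet *Possible* and the 4 with E = 0 meet *Definite*. All 8 count as related under every reading.
- Cut at *Probable* or higher: 8 of 8 count under reading 1, but 6 of 8 under readings 2 and 3.

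**Repairing only 'or' to 'and'.** *Definite* = T and D and not E is met by 2 patterns. One of them (K = 0) still fails *Probable*, and the new, unexplained event above now meets none of the three grades.

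**Repairing both.** If *Probable* = T and not E (4 patterns) and *Definite* = T and D and not E (2 patterns), both *Definite* patterns lie inside *Probable*. All 8 timed patterns have a grade: 4 meet *Possible* and 4 meet *Probable*, 2 of which also meet *Definite*. The new, unexplained event becomes *Probable*.

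**The case against.** The strongest reply is that the scale is guidance rather than an algorithm. Section 14.3.2 says so and asks for alternative causes to be weighed, so few investigators would call an event definite on timing alone. This stands: inconsistent grading is a risk, not a certainty. The scale is still the only definition the sites are given.

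A reader might infer four stronger conclusions that the documents do not support.

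- *That timing alone always earns Definite.* This holds only on the literal text. The sentence is garbled, a word may have been lost in drafting or in reading the PDF, and under two of three readings timing alone is not enough. The inversion itself survives all three.
- *That Probable can never be used.* Section 6.3 names possible hypersensitivity, and experience accrues before the expansion cohort. The grade is close to unreachable at the start, not throughout.
- *That the stopping rules misclassify events.* They use a plain 'related'. If that means *Possible* or higher, moving an event among the top three grades changes nothing. A rule changes only if the cut lies above *Possible*, or if an event is moved up from *Unlikely*. That one related serious event can stop a cohort of 4 or 5 follows from a one-event rule under any scale.
- *That serious events go unreported.* Sections 14.4.1 and 14.7 require all serious events to be reported within 24 hours, whatever their grade. Only the sentence on events discovered after the study is exposed, and most investigators would read it as including a stronger grade.

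Finally, the grouping of grades may be set in the separate SAP that Section 18 announces, and Section 8.4 leaves to the dose escalation committee charter which safety observations require a dosing decision. That is possible, but neither would repair the definitions in Section 14.3.2.

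**Conclusion.** The point holds in this form. *Definite* is looser than *Probable* under each reading tested (14, 6 or 10 patterns against 2), and a new, well-timed, unexplained event can be placed only in the top grade. This rests on taking the definitions as written and on there being little or no known human response at study start.

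What is at risk is the consistency of the five-level relationship tables for all AEs, ocular and non-ocular, together with the terms used in Sections 14.7 and 14.8. The primary endpoint, frequency and severity of ocular AEs (Section 7.2.1), does not use causality and is unaffected. No hypothesis test depends on the scale. An effect on the stopping criteria is conditional on a cut for 'related' that no section states, or on an event moving up from *Unlikely*. It should not be claimed as shown.

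**What to change.** - **Section 14.3.2:** repair the phrase 'or control abates', join the *Definite* conditions with 'and', and stop making a known response mandatory for *Probable*, so that *Definite* nests inside *Probable*. Both changes are needed, because the first alone leaves the new, unexplained event ungraded.
- **Sections 14.7 and 14.8:** add *Definite* to 14.7 and use the five grade names in 14.8.
- **Section 18.3.2:** state how the five grades are grouped as related or not related in the tables.
- **Sections 8.5.1.1, 8.5.2.1 and 8.5.2.2:** reconcile the word 'related' with the scale. Which grades should count there is for the sponsor to settle, and this review does not propose one.

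The cost is protocol and eCRF-guideline wording, with no new data or procedures. The small downside is that events already graded under the current text need a query.

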#### 14.3.3. Action Taken with Investigational Products

Should the Investigator need to alter the administration of the study drug from the procedure described in the protocol due to the well-being and safety of the subject then the action taken will be recorded on the AE eCRF page, as one of the following options:

- Drug Interrupted
- Drug Withdrawn
- Not Applicable
- Other

#### 14.3.4. Outcome

Outcome of an AE will be recorded on the AE eCRF as follows:

- Recovered / Resolved
- Recovering / Resolving
- Recovered / Resolved with Sequelae
- Not Recovered / Not Resolving
- Fatal
- Unknown

#### 14.4. Definition of Serious Adverse Event

An SAE is an AE occurring during any study phase (i.e., baseline, treatment, washout, or follow-up), and at any dose of the study drug (active or placebo), that fulfills one or more of the following:

- Results in death
- It is immediately life-threatening
- It requires at least a 24-hour in-patient hospitalization or prolongation of existing hospitalization
- It results in persistent or significant disability or incapacity
- Results in a congenital abnormality or birth defect
- It is an important medical event that may jeopardize the subject or may require medical intervention to prevent one of the outcomes listed above

Important medical events that may not be one of the above may be considered an SAE by the Investigator when, based upon appropriate medical judgment, they are considered clinically significant and may jeopardize the subject, or may require medical or surgical intervention to prevent one of the outcomes listed above.

Examples of such events are:

- Intensive treatment in an emergency room or at home for allergic bronchospasm
- Blood dyscrasias or convulsions that do not result in in-patient hospitalization
- Development of drug dependency or drug abuse

An AE is considered “life-threatening” if, in the opinion of either the Investigator or the Sponsor, its occurrence places the subject at immediate risk of death. It does not include an AE that, had it occurred in a more severe form, might have caused death.

Treatment within or admission to the following facilities is not considered to meet the criteria of “in-patient hospitalization” (although if any other SAE criteria are met, the event must still be treated as an SAE and immediately reported):

- Emergency Department or Emergency Room
- Outpatient or same-day surgery units
- Observation or short-stay unit
- Rehabilitation facility
- Hospice or skilled nursing facility
- Nursing homes, Custodial care or Respite care facility

Hospitalization during the trial for a pre-planned surgical or medical procedure does not require reporting as a SAE to the clinical research organization’s Safety Department.

#### **14.4.1. Notification of a Serious Adverse Event**

In order to meet the requirements for expedited reporting of SAEs meeting specific requirements to applicable regulatory authorities and IEC, all SAEs, **must be reported to [REDACTED] within 24 hours** from the time the site investigational team first become aware of the event.

**Initially reporting is achieved by completing an SAE report form and email to [REDACTED] via the assigned project email address, which will be provided upon study setup.**

If completion of an SAE form and emailing is not possible, reporting by telephone to [REDACTED] is required and a completed [REDACTED] SAE form must be emailed at the first opportunity.

Initial notification of an SAE by telephone to [REDACTED] must be confirmed in writing 24 hours from the time the site investigational team first becomes aware of the event using the SAE report form as described above.

As further information regarding the SAE becomes available, such follow-up information should be documented on a new SAE report form, marked as a follow-up report, scanned and emailed to the address at the bottom of the report form.

Withdrawal from the study in the event of an SAE and therapeutic measures taken shall be at the discretion of the Investigator. A full explanation for the discontinuation from the study should be made in the subject's medical records and in the eCRF.

#### **14.5. Clinical Laboratory Abnormalities and Other Abnormal Assessments as Adverse Events and Serious Adverse Events**

Abnormal laboratory findings (e.g., biochemistry, hematology, coagulation and urinalysis) or other abnormal assessments (e.g., ECG and vital signs) per se are not reported as AEs. However, those abnormal findings that are deemed **clinically significant** by the PI and/or delegate or are associated with signs and/or symptoms must be recorded as AEs if they meet the definition of an AE (and recorded as an SAE if they meet the criteria of being serious) as previously described. Clinically significant abnormal laboratory or other abnormal findings that are detected after consent or that are present at baseline and worsen after consent are included as AEs (and SAEs if serious).

The Investigator should exercise medical and scientific judgment in deciding whether an abnormal laboratory finding, or other abnormal assessment is clinically significant. To be considered clinically significant, the abnormality should be associated with a clinically evident sign or symptom or be likely to result in an evident sign or symptom in the near term. A clinically significant laboratory abnormality in the absence of clinical symptoms may jeopardize the subject and may require intervention to prevent immediate consequences. For example, a markedly low serum glucose concentration may not be accompanied by coma or convulsions yet be of a magnitude to require glucose administration to prevent such sequelae.

#### **14.6. Recording Adverse Events**

AEs spontaneously reported by the subject and/or in response to an open question from the study personnel or revealed by observation will be recorded in accordance with the Investigator's normal clinical practice and on the AE page of the eCRF during the study at the investigational site.

However, abnormal values that constitute an SAE or lead to discontinuation of administration of study drug must be reported and recorded as an AE. Information about AEs and SAEs will be collected from the time of consent until the end of the study. The AE term should be reported in

standard medical terminology when possible. For each AE, the Investigator will evaluate and report the onset (date and time), resolution (date and time), intensity, causality, action taken, serious outcome (if applicable), and whether or not it caused the subject to discontinue the study. AEs that occur during the study must be documented in the subject's medical record, on the AE eCRF and on the SAE report form. If an SAE report is completed, pertinent laboratory data should be recorded on the SAE form, preferably with baseline values and copies of laboratory reports.

In addition, if the abnormal assessment meets the criteria for being serious, the SAE form must also be completed. A diagnosis, if known, or clinical signs or symptoms if the diagnosis is unknown, rather than the clinically significant laboratory finding or abnormal assessment, should be used to complete the AE/SAE page. If no diagnosis is known and clinical signs or symptoms are not present, then the abnormal finding should be recorded.

It is important to distinguish between serious and severe AEs. Severity is a measure of intensity whereas seriousness is defined by the criteria under [Section 14.4](#). An AE of severe intensity may not be considered serious.

Should a pregnancy occur, it must be reported and recorded on a [REDACTED] pregnancy form. Pregnancy is not regarded as an AE unless there is a suspicion that a study drug may have interfered with the effectiveness of a contraceptive medication.

The outcome of all pregnancies (spontaneous miscarriage, elective termination, normal birth or congenital abnormality) must be followed up and documented even if the subject was discontinued from the study.

All reports of congenital abnormalities/birth defects are SAEs. Spontaneous miscarriages should also be reported and handled as SAEs. Elective abortions without complications should not be handled as AEs.

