## 7.2. Endpoints

### 7.2.1. Safety and Tolerability

The safety and tolerability endpoints of the study are:

- Primary:
  - Frequency and severity of ocular AEs in the study and contralateral eyes
- Secondary:
  - Frequency and severity of non-ocular AEs
  - Changes from baseline in safety parameters, including vital sign measurements, physical examination findings, ECG, and laboratory parameters
  - Changes from baseline in ophthalmic examination findings, including ophthalmoscopy.

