#### 8.5.1.1. Individual Subject Stopping Criteria

Any of the following criteria will be considered as stopping criteria for the study eye in individual subjects:

- An increase from baseline in CMT  $\geq 75 \mu\text{m}$  when seen across two consecutive visits
- A loss of  $\geq 15$ -letters of vision as determined by ETDRS, from the best previous in-study BCVA, due to DME, with current BCVA not better than baseline
- A loss of  $\geq 10$ -letters of vision from best previous in-study BCVA (determined by ETDRS), due to DME, seen across two consecutive visits, with current BCVA score not better than baseline
- Persistent intolerable ocular irritation or redness
- Development of persistent corneal opacities or severe keratitis

- An  $\geq 10\%$  increase in corneal thickness in the study eye based on pachymetry assessed at a consistent time of day
- Intraocular pressure (IOP) increase of 12 mmHg or more (from baseline measurements) confirmed upon repeat testing
- Occurrence of any severe graded AE that is assessed by the Investigator to be related to study drug
- Occurrence of any serious adverse event assessed by the Investigator to be related to study drug
- If a subject's CMT is 420  $\mu\text{m}$  or less, the subject is withdrawn from the study if there is BOTH a loss of BCVA of  $\geq 10$  letters AND an increase in CMT of  $\geq 50 \mu\text{m}$
- If a subject's CMT is  $>420 \mu\text{m}$ , the subject is withdrawn if there was also EITHER a loss of BCVA of  $\geq 10$  letters OR an increase in CMT of  $\geq 50 \mu\text{m}$
- The Investigator believes it is in the best interest of the subject to discontinue study drug dosing and/or initiate an anti-VEGF or other rescue therapy.

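### Mandatory AE recording under Section 14.6 falls mainly on study-eye findings during dosing, so asymptomatic eye findings may be captured unevenly by eye and study part

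*Combined protocol and SAP*

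**What the plan says.** The primary endpoint in Section 7.2.1 is "Frequency and severity of ocular AEs in the study and contralateral eyes". Section 18.3.2 tabulates ocular TEAEs by treatment group and by eye. Section 8.1 also plans a within-subject comparison with the undosed eye and a group comparison with pooled vehicle subjects.

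Two sections govern when an abnormal assessment is an AE.

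- **Section 14.5, the general rule.** Laboratory findings and "other abnormal assessments (e.g., ECG and vital signs) per se are not reported as AEs". Findings judged clinically significant "or are associated with signs and/or symptoms must be recorded as AEs if they meet the definition of an AE". The test is that "the abnormality should be associated with a clinically evident sign or symptom or be likely to result in an evident sign or symptom"; the second alternative is limited to the short term. Clinically significant "findings that are detected after consent or that are present at baseline and worsen after consent are included as AEs". Nothing here depends on eye, study part, visit or dosing, and no eye measurement or numeric limit is named.
- **Section 14.6, a mandatory addition.** It says that "abnormal values that constitute an SAE or lead to discontinuation of administration of study drug must be reported and recorded as an AE". There are two limbs: SAE, and stopping of study drug.

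Section 8.5.1.1 opens with "Any of the following criteria will be considered as stopping criteria for the study eye in individual subjects" and then lists numeric criteria for CMT, BCVA, corneal thickness and IOP.

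**The concern.** The second limb of Section 14.6 ties AE status to a treatment decision. A measured change in the study eye that stops drug must be recorded, symptoms or not. The same asymptomatic change in the contralateral eye, or in the study eye after the last dose, rests on Section 14.5 judgment alone. The clearest cases are an IOP rise, corneal thickening and a CMT rise, which a subject may not notice.

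At stake is how the by-eye AE table can be read. Part of any excess in the study eye could come from how findings are recorded. Vehicle subjects dosed for 7 days and for 84 days would also be pooled although the limb reaches them differently. Findings first seen at the end of 84 days' exposure lie outside the limb.

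**Working it through.** No stated sample size, power or event rate bears on this point, so there is no plan figure to reproduce. The check compares the recording rules with the visit schedule.

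**1. When can the discontinuation limb act?** Dosing ends on Day 7 in escalation (Section 6.4.1; 7 × 2 = 14 doses) and after 84 days in expansion (Section 12.4.1.2; 84 × 2 = 168 doses). Nominal eye assessments after Day 1, from Table 5 and Section 12:

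| Assessment | Escalation: all days | During dosing | Expansion: all days | During dosing |
|---|---|---|---|---|
| SD-OCT (CMT) | 8, 36 | none | 8, 29, 57, 85, 113 | 8, 29, 57 |
| BCVA | 8, 36 | none | 8, 15, 29, 57, 85, 113 | 8, 15, 29, 57 |
| Pachymetry | 8, 36 | none | 29, 57, 85, 113 | 29, 57 |
| IOP | 3, 4, 8, 36 | 3, 4 | 8, 29, 57, 85, 113 | 8, 29, 57 |
| Ophthalmic exam | 3, 4, 8, 36 | 3, 4 | 8, 29, 57, 85, 113 | 8, 29, 57 |
| CFP | 8, 36 | none | 8, 29, 57, 85, 113 | 8, 29, 57 |

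Totals during dosing: 4 of 16 (25%) in escalation and 18 of 30 (60%) in expansion. IOP and the ophthalmic exam are also repeated after the first dose on Day 1. The ±2-day window at Day 85 could move individual subjects.

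**2. Two-visit requirement.** The 75 µm CMT criterion must be seen at two consecutive visits. It can first be met on drug at Day 29 in expansion, and never in escalation. To be confirmed by Day 57, it must be first seen by Day 29. If onset is assumed uniform over Days 1–113, the on-drug share is (29 − 1)/112 = 25%; over Days 1–84 it is 28/83 = 34%. Without the two-visit requirement the shares would be 56/112 = 50% and 56/83 = 67.5%. The combined CMT-and-BCVA criteria in the same list have no two-visit requirement.

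**3. Size under assumed inputs.** None of these values is in the documents. Take an inert drug and N = 40. Let p be the chance of an asymptomatic crossing, equal in both eyes; c the share recorded under Section 14.5; and f the share of the rest that stops drug in the study eye.

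Excess study-eye AE subjects = N × p × (1 − c) × f.

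With p = 0.10 and f = 0.6:
- c = 0: 40 × 0.10 × 1 × 0.6 = 2.4
- c = 0.5: 40 × 0.10 × 0.5 × 0.6 = 1.2
- c = 0.9: 40 × 0.10 × 0.1 × 0.6 = 0.24
- c = 1: 0

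Over p = 0.05–0.20, c = 0–1 and f = 0.25–1 the range is 0 to 8 (maximum 40 × 0.20 × 1 × 1). In escalation, f is 0 for the listed CMT, BCVA and pachymetry criteria on the nominal schedule.

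**4. Pooling.** Escalation has 2 + 1 + 1 = 4 planned vehicle subjects. An expansion cohort of 40 at 2:1 has about 40/3 ≈ 13. Escalation would then supply about 4/17 = 24% of pooled vehicle subjects. At the expanded dose it would supply about 3/(3 + 27) = 10% of active subjects, if those are pooled too.

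**5. Do the planned summaries fill the gap?** Only in part. Section 18.3.6 gives values and changes by group, visit and eye for CMT, BCVA and corneal thickness, but its list omits IOP. It has no count of subjects crossing a CMT or corneal-thickness threshold. Its BCVA proportions use change from baseline, whereas the Section 8.5.1.1 letter-loss criteria start from the best previous in-study score. Section 18 leaves unscheduled data out of summaries unless stated otherwise, so an unscheduled repeat confirming an IOP rise could drop out.

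**The case against.** The strongest reply is that Section 14.6 only adds a floor. Section 14.5 is the main rule and is neutral to eye and visit, and the SAE limb does not depend on dosing. Section 14.2 collects AEs from consent to EOS. Section 14.3 counts any unfavourable sign, and exacerbation of a pre-existing condition, as an AE. Worsening DME fits that in either eye, and a 10- to 15-letter loss will often be noticed. All of this stands. A reader might infer that the same finding is an AE in one eye and not in the other. The documents do not support that: outside the floor the finding is left to judgment, not excluded.

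A reader might also infer that a contralateral-eye finding can never trigger the limb. That is too strong:
- the synopsis allows stopping for any AE, systemic or ophthalmic;
- Section 8.5.1 allows withdrawal whenever safety is compromised;
- the best-interest criterion in Section 8.5.1.1 names no finding, though it sits under the study-eye heading;
- Section 8.5.3 makes remaining in the study after fellow-eye treatment discretionary.

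The treatment comparison is active versus vehicle. Within a part, both masked arms share the same visits, rules and eye definition, so the rule itself creates no arm-specific bias. This stands too.

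Finally, the measured values are reported anyway. That holds in part, with the gaps shown in step 5 of the working. Section 18.4 is blacked out and the separate SAP is not in the text, so either may hold more.

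**Conclusion.** The point holds in limited form. For asymptomatic eye findings, Section 14.5 offers no objective criterion, and the mandatory recording in Section 14.6 falls mainly on the study eye during dosing. Ascertainment can therefore differ between eyes and between study parts, most plausibly for IOP, corneal thickness and CMT. The by-eye AE comparison and any pooling of vehicle across parts are exposed; active versus vehicle within a part is much less so.

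The size cannot be derived from the documents, and the 0-to-8 range includes no effect. A reader might want to quote a spurious study-to-contralateral ratio. With a 20% crossing rate in each eye, half of crossings seen on drug and 20% judged significant, the rates would be 0.20 × (0.5 + 0.5 × 0.2) = 12% against 0.20 × 0.2 = 4%, a ratio of 3. That figure should not be used, for three reasons:
- It assumes that every on-drug crossing stops drug. The synopsis and Section 8.1 say subjects *will* be discontinued, while Section 8.5.1 says they *may* be; these passages must be reconciled.
- It ignores the two-visit CMT requirement. With 25% on drug the rates are 0.20 × (0.25 + 0.75 × 0.2) = 8% against 4%, a ratio of 2.
- It treats the eyes as exchangeable. The study eye must have center-involved DME and is the one with greater CMT if both qualify; the other eye need not have DME.

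The conclusion rests on nominal visit days and on some asymptomatic findings not being judged clinically significant.

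**What to change.** In Section 18.3.6:

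1. Add IOP to the summarized assessments, by group, visit and eye.
2. Add one table of subjects whose change in CMT, BCVA, corneal thickness or IOP meets the existing numeric thresholds in Section 8.5.1.1. It should cover any visit after the first dose through EOS, include unscheduled confirmatory measurements, and be split by arm, study part and eye, regardless of AE status or dosing status. Read it beside the by-eye ocular AE table.

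The protocol requires all evaluations in both eyes (Section 12.1.1), so no new assessment is needed. No AE-recording, stopping, dosing or rescue rule changes. The synopsis words the CMT criterion differently from Section 8.5.1.1 (above 75 µm, with no two-visit condition), so those passages need reconciling before the table is programmed.

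The cost is one more table, which will include natural DME worsening in both arms and should carry a footnote saying so. Making every threshold crossing an automatic AE would also even out the recording. But it would put natural worsening into the primary endpoint and replace the judgment that Section 14.5 assigns to investigators, so it is not proposed here.
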